5.3 Concomitant therapy

5.3.1 Premedication

Corticosteroids are administered at the treating physician's discretion. This could be important, because the relevance of "edema" will be taken into consideration by the neuroradiologist. Steroid dose must be stable within 14 days prior to study registration or decreasing 5 days prior to registration.

5.3.2 Prophylaxis

Antiemesis

A prophylactic standard antiemetic regimen using a serotonin antagonist (e.g. ondansetron, tropisetron) prior to administration of the chemotherapeutic agents CCNU and TMZ is mandatory.

Lymphocytopenia

In case of lymphopenia $<500/\mu\text{l}$ during CCNU/TMZ or the adjuvant therapy phase of TMZ monotherapy, prophylactic treatment with trimethoprim and sulfamethoxazol (e.g. Cotrim forte®) should be started with Trimethoprim 160 mg, Sulfamethoxazol 800 mg

(e.g. Cotrim forte®) three times a week. Additionally, prophylactic trimethoprim/sulfamethoxazol therapy according to this regimen is mandatory during standard daily concomitant TMZ therapy.

Neutropenia

Afebrile Neutropenia

In case of ANC < 500 / μ l without fever or infection, prophylactic antibiotic therapy with ciprofloxacin should be started, in case of rapid decrease of ANC prophylaxis could be started before the threshold of 500 / μ l. Patients with neutropenia < 500 / μ l lasting more than 7 days should be given additional antimycotic prophylaxis with itraconazol-suspension 5 mg/kg twice daily (as long as neutrophil counts are < 1000 / μ l). Particular attention should be paid to potential contraindications of a treatment with itraconazol, e.g. drugs prolonging QT-interval. Patients with neutropenia <500/ μ l should also receive G-CSF (e.g. Granocyte®) 19,2 Mio IE (150 μ g) /m²/day until neutrophil counts reach 1500/ μ l.

Febrile Neutropenia

In case of neutrophil counts < 500 / μ l with fever and/or infection patients should be admitted to the hospital and treated with piperacillin 4g and tazobactam. Septic patients should be given gentamicin (Refobacin®) 3 mg/kg additionally (ototoxicity and nephrotoxicity to be considered) once a day. Hematopoietic colony-stimulating factors like Lenograstim (e.g. Granocyte®) 19,2 Mio IE (150 μ g) /m² should be given once a day until neutropenia is resolved (ANC >1500/ μ l). In case of persisting fever and absent detection of pathogens, antibiotic therapy should be switched to meropenem (Meronem®) 1 g t.i.d.. Vancomycin 1 g b.i.d. might be added. Patients with neutropenia < 500 / μ l lasting more than 7 days should be given additional antimycotic prophylaxis with itraconazol-suspension (see above). In case of lymphocyte counts < 500 / μ l Trimethoprim 160 mg, Sulfamethoxazol 800 mg (e.g. Cotrim forte®) three times a week.

5.3.3 Other concomitant medication

In general, concomitant medications and therapies deemed necessary for the supportive care and safety of the patient are allowed, provided their use is documented in the patient records and on the appropriate CRF. All concomitant medications,

received from 30 days prior to study entry until completion/early withdrawal, will be recorded in the CRF at each visit. The information should include the name of the drug, indication for use in this patient, daily dose, and the start and stop date(s) of administration.

The administration of any other anticancer agent is NOT permitted. This also applies to agents with hypothetical anticancer effects such as St John's wort extracts, high-dose vitamin therapy, Boswellia acids, any sort of immunotherapy. Similarly, the use of other investigational drugs, experimental radiotherapy beyond standard radiotherapy (stereotactic boost, hyperfractionated radiotherapy) or hyperthermia is not allowed. Patients may receive, at the discretion of the investigator, appropriate medical and surgical treatment that is not specifically prohibited by this protocol. If a patient has or develops hypertension, therapy with an angiotensin converting enzyme inhibitor or angiotensin II antagonist is recommended. Patients with liver enzyme-inducing antiepileptic agents are encouraged to switch to non-enzyme-inducing agents (levetiracetam, gabapentin, lamotrigin). Treatment with steroids should be registered (dose, day).

5.4 Duration of Therapy

Treatment cycles will be repeated until progression or unless unacceptable toxicity is encountered. A maximum of 6 cycles of CCNU/TMZ will be administered. After the completion of CCNU/TMZ therapy with a maximum of 6 courses, the patient will be followed by neurological examination and MRI every 3 months. In case of recurrent disease, salvage therapy is chosen at the discretion of the treating physician.

If a patient progresses while on treatment further therapy is at the discretion of the treating physician.

6. CLINICAL EVALUATION, LABORATORY TESTS, FOLLOW-UP

6.1 Study procedures

The attached Time and Events Schedule (Table 2) summarizes the frequency and timing of the various investigations and safety measurements. The neuroradiologic evaluation of response must be performed by contrast-enhanced MRI. A deviation of more than 5 days regarding the defined timepoints for each visit is regarded as a

protocol violation. This does not apply to the delay of chemotherapy courses due to prolonged toxicity in the previous course. The therapeutic options for patients who progress during study treatment are not determined by this protocol, but according to our previous experiences ([name] et al., 2006), intensified TMZ chemotherapy according to the one week on/off schedule (Wick et al., 2007) is recommended. To ensure reproducibility of MRI evaluation, all MRIs have to be reviewed by the reference neuroradiologist [name]. [name], Division of Neuroradiology, Department of Radiology, [name]. The MRIs have to be sent blinded (only labelled with Pat.-ID) to the reference neuroradiologist to ensure unbiased progression assessment.

In particular, the study visits include the following items:

- **Screening visit (week 1-3 after resection):**
 - Written informed consent for neuropathology reference testing and for MGMT testing

- **Baseline visit (week 3 to 5 after resection):**
 - Written informed consent for the trial
 - Inclusion/exclusion criteria (including MGMT and reference neuropathology test result)
 - Medical history and demographics
 - Vital signs
 - physical and neurological examination
 - concomitant medication
 - Karnofsky PS
 - Mini-Mental-Status evaluation and neurocognitive testing (NOA-07 test battery)
 - quality of life questionnaire
 - baseline contrast enhanced MRI scan (all post surgery MRIs not older than 3 weeks can be taken as baseline MRI (ideally early post surgery (72h))
 - ECG
 - spirometry
 - pregnancy test for women with reproductive potential
 - complete blood count and CRP
 - Blood sampling for translational studies

- serum chemistry and urine analysis
 - coagulation
 - Documentation of preexisting conditions in analogy to CTCAE
 - Randomisation
- **At the beginning of each course of CCNU/TMZ or TMZ:**

(Standard arm (TMZ): visit can be done within 5 days before start of cycle;
Experimental arm (CCNU/TMZ): visit has to be done on day of cycle start.
Before start of chemotherapy (concomitant TMZ or first cycle CCNU/TMZ: blood analysis obtained in Baseline can be used if not longer than 5 days old)

 - Assessment of survival
 - vital signs,
 - physical and neurological examination,
 - concomitant medication,
 - Karnofsky PS,
 - complete blood count and CRP,
 - serum chemistry and urine analysis,
 - coagulation,
 - CTCAE evaluation

Throughout all treatment courses of TMZ and CCNU/TMZ starting with radiotherapy a differential blood count has to be determined weekly by the general practitioner of each patient. The results have to be faxed within 24 hours to the treating center for review. In case pathological laboratory values are regarded by the local investigator to have medical consequences (e.g. grade 4 neutropenia requiring prophylactic antibiotic treatment) the differential blood count has to be repeated at the study center.

- **MRI/ progression assessment visits every 12 weeks (+/- 5 days) after randomization during study treatment and follow up until end of study**
- (Follow-up of all patients ends 36 months after the inclusion of the last patient. All patients in the trial are followed until this time point.)
 - vital signs
 - physical and neurological examination

- concomitant medication (all medication during the treatment phase, during follow-up this includes only the tumor-related medication)
- further tumor-directed therapy (surgery, radiotherapy, chemotherapy): day of start of further therapy, day of progression for each therapy
- Karnofsky PS
- Mini-Mental-Status evaluation
- quality of life questionnaire
- contrast-enhanced MRI scan
- NOA-07 test battery (only every 24 weeks)
- complete blood count and CRP
- Blood sampling for translational studies
- serum chemistry and urine analysis
- coagulation
- CTCAE evaluation
- Assessment of progression/survival

Table 2: Schedule of Study procedures

	Screening visit Week 1-3	Baseline visit Week 3-5 ⁽²⁾	Treatment phase		After 6 courses of CCNU/TMZ or TMZ
			At the beginning of each course of CCNU/TMZ or TMZ	MRI/progression assessment visit every 12 weeks ⁽¹⁾	MRI/progression assessment visit every 12 weeks ⁽¹⁾
Clinical examination					
Informed consent for MGMT and reference neuropathology ⁽³⁾⁽³⁾	x				
Informed Consent for trial participation		x			
Results of MGMT testing and ref. neuropathology		x			
I / E criteria, demographics and medical history		x			
Evaluation of preexisting conditions in analogy to CTCAE		x			
Vital signs: BP, P, T, height, weight ⁽¹⁾		x	x	x	x
Physical and neurological examination		x	x	x	x
Concomitant medication		x	x	x	X5
Karnofsky PS		x	x	x	x
MMSE		x		x	x
NOA-07 test battery		x		x (every 24 weeks)	x (every 24 weeks)
QoL: EORTC QoL C30 and BN20		x		x	x
CTCAE evaluation		x	x	x	x
MRI and response assessment					
Gd-MRI		x		x	x
Progression/survival				x	x
Laboratory Testing					
Spirometry		x			
Serum pregnancy test ⁽⁴⁾		x			
CBC with differential and CRP		x	x	x	x
Serum chemistry ⁽⁵⁾ and urinalysis, coagulation		x	x	x	x
Blood sampling for translational studies		x		x	x

Abbreviations: BP = blood pressure, CTCAE = common terminology criteria for adverse events, ECG = electrocardiogram, Gd = gadolinium-enhanced, I/E = inclusion/exclusion criteria, MRI = magnetic resonance imaging, MMSE = Mini Mental State Examination, NOA-07 test battery short neuropsychological test, PS = performance score, T = temperature

Comments: (1) Within 5 days before or after scheduled visit. (2) Baseline assessment to be performed ≤ 21 days prior to start of RT. (3) for trial, MGMT testing and reference neuropathology ≤ 21 days prior to start of study treatment. (4) For women with reproductive potential ≤ 14 days prior to enrollment. (5) Including ASAT, ALAT, gammaGT, AP, amylase, lipase, creatin kinase, total bilirubine, C-reactive protein, creatinine, Na, K, Ca, TSH.(5) Only tumor-directed comedication

6.2 Efficacy Evaluations

6.2.1 Definition of Efficacy Criteria

Response and progression will be evaluated using the response criteria defined by the Response Assessment in Neuro-Oncology Working Group (RANO, Wen et al., 2010). The measure of "size" of contrast-enhancing lesions on T1-weighted scans is the largest cross-sectional area (largest cross-sectional diameter x largest diameter perpendicular to it). Measurable lesions are defined as lesions with two perpendicular diameters of at least 10 mm, visible on two or more axial slices. The cystic or surgical cavity should not be measured in determining response. In case of multiple lesions, a maximum of five of the largest lesions may be measured.

T2 and/or FLAIR hyperintensities are also evaluated for response and progression. T2/FLAIR hyperintensities are only graded as "decreasing", "stable" or "increasing" and are, according to the RANO criteria, not formally quantified. In general, "increasing" T2/FLAIR hyperintensities qualifying for progressive disease can only be diagnosed if it may be attributed to tumor growth (e.g. mass effect such as sulcal effacement, thickening of the corpus callosum, infiltration of the cortical ribbon or location outside the radiation field) AND other causes for increased T2/FLAIR hyperintensities are unlikely such as radiation effects, decreased corticosteroid dosing, demyelination, ischemic injury, infection, seizures, postoperative changes or other treatment effects. In unclear cases, a repeat MRI 4 weeks later is recommended.

Clinical criteria such as neurological status and steroid usage are also taken into account to determine response and progression. The neurological status is graded as "improving", "stable" or "worsening". Steroid usage is not taken into account for the definition of progressive disease (PD). In general, to label the neurological status as "worsening", it should be unlikely that the deterioration of the neurological status is caused by comorbid events such as radiation therapy, reduction or termination of steroid dosage, comedication adverse events, cerebrovascular events, complications of therapy, infection, seizures, postoperative changes or other treatment effects. Clinical worsening has to be present for 7 days or more. Clinical progression should be always

further substantiated by demonstration of progressive contrast.-enhancing lesions on MRI.

The RANO criteria are in general as follows:

- **Complete Response (CR):** Disappearance of all measurable contrast enhancing lesions in magnetic resonance imaging at least 4 weeks apart, T2/FLAIR lesions stable or decreasing, without steroids and neurologically stable or improved.
- **Partial Response (PR):** At least 50% reduction in the size of all measurable contrast enhancing lesions in magnetic resonance imaging at least 4 weeks apart, T2/FLAIR lesions stable or decreasing, steroids stable or reduced, and neurologically stable or improved.
- **Stable disease:** Less than 50% reduction or less than 25% increase in the size of a solid mass or all contrast enhancing lesions in magnetic resonance imaging, with no escalation of steroid treatment and no neurological deterioration.
- **Progression:** At least 25% increase in the size of measurable contrast enhancing lesions in magnetic resonance imaging OR clear increase of a non-measurable lesion or the appearance of a new lesion OR significantly increasing T2/FLAIR hyperintensities (only if other causes for increased T2/FLAIR hyperintensities are unlikely such as radiation effects, decreased corticosteroid dosing, demyelination, ischemic injury, infection, seizures, postoperative changes or other treatment effects) OR clear and significant worsening of the neurological status not attributable to other causes apart from the tumor (see above)

For the interpretation of the study's results we introduced some modifications of the RANO criteria (referred to as "modified RANO criteria") as the following restrictions in the RANO response assessment apply to MRI and clinical controls in the early phase of the treatment:

- It is important to note that due to the tendency of MGMT-methylated GBMs to develop pseudoprogression (Brandes et al., 2008), progression of contrast-enhancing lesions or T2/FLAIR lesions in the first MRI after completion of radiotherapy (scan scheduled for week 12) or in any unscheduled clinical and/or MRI examination up to 12 week after completion of radiotherapy is only regarded as progressive disease (PD) if one of the following criteria apply
 - new enhancement outside the radiation field (i.e. beyond the 80% isodose)

- unequivocal evidence of viable tumor on histopathologic sampling (after re-surgery)
- Since in some cases treated with CCNU/TMZ (Stuplich et al., in preparation), pseudoprogression may even ensue later than 12 weeks after the end of radiotherapy, i.e. up to the second scheduled clinical and MRI control examination 24 weeks after randomization, PD can only be diagnosed between week 12 after the end of radiotherapy and the scheduled clinical and MRI examination visit 24 weeks after randomization inclusively if progression according to the RANO criteria given above is confirmed in a scan 4 to 6 weeks after the scan suggesting progression. Therapy within the trial has to continue until confirmation of progression in the MRI scan 4 weeks later. If PD is confirmed, the earliest timepoint at which the criteria for PD had been fulfilled will be taken as the timepoint to calculate progression-free survival.

In any case PD is diagnosed in the local center according to the criteria given above, all MRIs starting with the baseline MRI have to be immediately sent to the reference neuroradiologist [name]. [name], Division of Neuroradiology, Department of Radiology, [name]. The MRIs have to be sent blinded (only labelled with Pat.-ID) to the reference neuroradiologist to ensure unbiased progression assessment. Therapy within the trial has to continue until confirmation of progression in the MRI scan by the reference neuroradiologist.

6.2.2 Definition and evaluation of efficacy endpoints

Overall survival (Primary endpoint): Survival is defined as the duration from randomization to the date of death due to any cause.

Progression-free survival: The progression-free survival is defined as the time from randomization to the first documented evidence of progression of disease according to the modified RANO criteria.

Overall Response: The overall response rate is defined as the relative proportion of patients with complete and partial responses.

Time to Treatment Failure: Time to treatment failure is defined as the duration from the day of diagnosis (surgery obtaining histology) to any of the following:

- Death for any reason
- relapse or progressive disease (PD) during or after study treatment,
- discontinuation of combined CCNU/TMZ treatment for any reason before the completion of 3 cycles CCNU/TMZ

Frequency of delay of the next CCNU/TMZ or TMZ course by more than 2 weeks

Quality of Life: The EORTC QoL questionnaire modules QLQ-C30 and BN20 will be used to assess the quality of life. These assessments will be performed on the visits specified in the Time and Events Schedule. Patients will be given these questionnaires to complete by a study center staff member. The staff member will collect each completed assessment and check it for completeness before giving the patient the next assessment to complete.

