The combination of CCNU and TMZ may have an at least additive antiproliferative and proapoptotic effect on GBM cells. Further *in vitro* analyses in primary GBM cell cultures regarding the particular mechanism of CCNU/TMZ combination chemotherapy are ongoing. The particular design of the regimen (single dose of CCNU, TMZ given on 5 consecutive days) appears to play a role for the success of the regimen. Our schedule that combines CCNU on day 1 with TMZ (100 mg/m²/d) on the 5 consecutive days appears to be more effective than combinations of another nitrosourea compound, BCNU, and a single application of TMZ (550 mg/m²) which was not substantially more active than TMZ alone in patients with recurrent GBM (Prados et al., 2004) and had only modest activity in newly diagnosed anaplastic glioma (Chang et al., 2004). In contrast, Barrié et al. (2005) reported that with a schedule (BCNU 150 mg/m² day 1 + TMZ 110 mg/m²/d days 1-5) similar to our schedule, high objective response rates were seen in inoperable newly diagnosed GBM and a comparably long mOS (12.7 months) was observed in this prognostically unfavourable group.

Since the benefit of a new therapy is not only defined by efficacy in terms of survival prolongation but also by short-term and long-term side effects, it is important to know that acute hematotoxicity of the CCNU/TMZ regimen was tolerable and transient, albeit higher than with standard TMZ therapy: high-grade myelotoxicity occurred in 42% of patients and toxic death in 1/31 patients ([name] et al., 2006). Fortunately, no unexpected organ toxicity was recorded: 3/31 patients experienced transient nitrosourea-associated organ toxicity (grade 2 lung fibrosis, grade 3 asymptomatic elevation of transaminases, grade 4 CCNU-induced hepatitis). The long-term evaluation of surviving patients in the phase II trial and in another pilot trial showed that none of the long-term surviving patients experienced late neurotoxicity impairing the performance score. Thus, the survival-prolonging effect of CCNU/TMZ is not associated with quality of life-reducing late neurotoxicity.

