2.3 End-points

Primary end-point:

- Overall survival (OS) as measured from the day of randomization until death
-

Secondary endpoints:

- Progression-free survival (PFS) as measured from the day of randomization until diagnosis of progressive disease determined by MRI (modified RANO criteria)
- Best response rate determined by MRI (modified RANO criteria)
- Frequency of delay of the next CCNU/TMZ or TMZ course by more than 2 weeks
- Acute toxicity during radiotherapy and chemotherapy according to CTC AE V4.0
- Quality of life, determined by EORTC QLQ questionnaires
- Evaluation of late neurotoxicity by MMSE and NOA-07 test battery.
- Time to treatment failure

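### PFS is defined without death as an event, so the endpoint as written is time to progression, and the handling of deaths without documented progression is left open

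*Protocol*

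**What the plan says.** PFS is defined three times. Section 2.3 lists "Progression-free survival (PFS) as measured from the day of randomization until diagnosis of progressive disease determined by MRI (modified RANO criteria"), and the synopsis uses the same wording. Section 6.2.2 refers to the criteria rather than to MRI: PFS is "defined as the time from randomization to the first documented evidence of progression of disease according to the modified RANO criteria". None of the three names death.

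Section 6.2.2 does name death for its neighbours. For OS, "Survival is defined as the duration from randomization to the date of death due to any cause". For time to treatment failure, the first listed event is "Death for any reason". The abbreviation list has separate entries for PFS and for time to progression.

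Section 9.3 summarizes OS and PFS by Kaplan-Meier curves with medians and 95% confidence intervals. Its Kaplan-Meier rule censors patients who are still alive and patients lost to follow-up. A separate sentence censors dropouts at the time of dropout. Neither mentions a patient who died without progression.

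Section 6.2.1 restricts progression early on. Up to 12 weeks after radiotherapy, growth of enhancing or T2/FLAIR lesions "is only regarded as progressive disease (PD) if one of the following criteria apply": new enhancement outside the radiation field, or histological proof of viable tumor. From then to the week-24 visit, progression must be confirmed on a scan 4 to 6 weeks later.

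**The concern.** An endpoint called progression-free survival is normally read as time alive and free of progression. The endpoint defined here is something else, and a report that follows the protocol would put one quantity under the name of another.

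The protocol also supports two analyses. Followed literally, the definition gives a patient who dies without progression no event, so that patient is censored at death. The Kaplan-Meier rule, which censors only the living and the lost, can be read as not censoring that patient. In an open-label trial this choice should not remain open.

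PFS superiority is a stated secondary objective (Section 2.2), and Section 1.2 expresses the expected patient benefit as a 50% prolongation of PFS. Section 1.1 reports higher hematotoxicity with CCNU/TMZ than with standard TMZ, and "toxic death in 1/31 patients". Whether a toxic death counts in PFS therefore matters to the comparison.

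**Working it through.** **1. The plan's own figures.** The protocol gives no PFS sample size or event number; its figures rest on OS. Inputs from Section 9.1: death rates 0.356 and 0.176 per patient year, 64 per arm, accrual A = 2 years, original follow-up F = 2 years. The expected proportion dying in an arm is 1 − [exp(−λF) − exp(−λ(A+F))]/(λA).
- λ = 0.356: 0.649
- λ = 0.176: 0.407
- Events: 64 × (0.649 + 0.407) = 67.6, against 68 stated.
- Power with 68 events at a hazard ratio (HR) of 0.5 (Schoenfeld): Φ(√68/2 × ln 2 − 1.96) = 81.5%, against 80% stated.

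The figures reproduce. None uses PFS, so changing its definition leaves them as they are.

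**2. The definitions side by side.**

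| Endpoint | Where | Death an event? |
|---|---|---|
| OS | 6.2.2 | Yes |
| Time to treatment failure | 6.2.2 | Yes |
| PFS | Synopsis, 2.3, 6.2.2 | Not named |

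Section 6.2.2 names death where it is meant to count, so it is hard to read it as implied for PFS.

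**3. How a death without qualifying progression can arise.** Radiotherapy lasts 6 weeks and starts within 2 weeks of randomization, so 12 weeks after its end is week 18 to 20 after randomization. Until then lesion growth needs one of two specific proofs. After that, progression seen up to week 24 needs a scan 4 to 6 weeks later, as late as week 28 to 30. A patient who progresses and dies before that scan does not meet the definition.

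**4. Toxic deaths.** 64 × 1/31 = 2.1 experimental-arm patients. The rate rests on one event: its exact 95% interval (Clopper-Pearson, x = 1, n = 31) is 0.08% to 16.7%, or 0.05 to 10.7 of 64. The synopsis stopping rule tolerates 2 such deaths in the first 30 patients of an arm: 64 × 2/30 = 4.3.

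**5. Illustration of size.** Simulation with 4,000 patients per arm. Assumptions: exponential progression times; progression HR 2/3 (from the 50% prolongation in Section 1.2); control median 9 or 18 months; toxic deaths in the experimental arm only, within 36 weeks; no other deaths without progression.

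| Toxic deaths | Control median assumed (months) | HR: death censored / counted | Experimental median in months: death censored / counted |
|---|---|---|---|
| 1/31 | 9 | 0.646 / 0.669 | 13.8 / 13.1 |
| 1/31 | 18 | 0.669 / 0.701 | 27.3 / 25.9 |
| 2/30 | 9 | 0.653 / 0.699 | 13.5 / 12.1 |
| 2/30 | 18 | 0.674 / 0.737 | 27.2 / 24.4 |

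Counting death raises the HR by 0.02 to 0.06 and shortens the experimental-arm median by 0.7 to 2.8 months. If a further 10% of progressions in both arms end in undocumented death (1/31, 9 months), censoring lengthens both medians: 9.0 to 10.1 months in control and 13.0 to 15.3 in experimental.

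**6. Direction across all deaths.** Deaths by week 18 at the planning rates: 1 − exp(−0.356 × 18/52) = 11.6% and 1 − exp(−0.176 × 18/52) = 5.9%, or 7.4 control and 3.8 experimental patients of 64. With 0.272 and 0.136, assumed as roughly consistent with the blinded pooled rate of 0.1994: 9.0% and 4.6%, or 5.8 and 2.9. Adding toxic deaths on top of the experimental figure:
- 1/31: 3.8 + 2.1 = 5.9 against 7.4; 2.9 + 2.1 = 5.0 against 5.8. Control still has more.
- 2/30: 3.8 + 4.3 = 8.1 against 7.4; 2.9 + 4.3 = 7.2 against 5.8. The order reverses.

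The sign depends on assumptions that the protocol does not settle.

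**The case against.** The strongest defence is that the gap has little reach. PFS is secondary, OS is the only confirmatory test and counts every death, and Section 9.3 plans Kaplan-Meier summaries for PFS and exploratory Cox models. Time to treatment failure already captures death. All of this stands, and it limits the severity.

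A second defence is that a later analysis plan, promised in Section 9.3, would settle censoring. That holds for detailed censoring rules. It does not cure a definition that the protocol itself states three times.

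Several stronger readings are tempting, and the document does not support them:
- A reader might infer that deaths without progression are censored as successes. No section says they are censored, and a censored patient leaves the risk set without being counted as a success. The accurate worry is potentially informative censoring.
- A reader might infer that the rule favors the experimental arm. That holds for toxic deaths taken alone. For all early deaths the sign is open (step 6).
- A reader might infer that most patients who die early cannot have a progression event. Out-of-field enhancement and histology remain as routes. Section 6.2.1 also lists neurological worsening as progression, though it asks for MRI support, and the synopsis and Section 2.3 require MRI.
- The week-18 percentages are not counts of affected patients. They are all-cause deaths under a constant hazard, while entry requires a Karnofsky score of at least 70% and a life expectancy of at least 12 weeks. The share without progression is not given.

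The early restriction itself is a deliberate safeguard against pseudoprogression, explained in the text, and is not an error.

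**Conclusion.** The point holds for the definition. All three statements of PFS omit death, so the endpoint is time to progression under another name, and Section 9.3 leaves deaths without documented progression unassigned. The early modified RANO restrictions make such deaths more likely.

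Toxic deaths at the phase II rate would be about 2 of 64 experimental patients, a very uncertain figure, and on the literal reading would not count against PFS in that arm. The illustrated HR shift of 0.02 to 0.06 rests on toxic deaths in that arm only and on the assumed HR and medians. It shows the possible size for one type of death, not a net bias. The net direction cannot be determined from the protocol.

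This should be corrected before analysis, but it is not critical to the trial: OS, the 68 events, the sample size and the power do not change.

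**What to change.** - In the synopsis, Section 2.3 and Section 6.2.2, define PFS as time from randomization to progression by the modified RANO criteria or death from any cause, whichever comes first.
- In Section 9.3, state that for PFS, patients alive without progression are censored at their last progression assessment.
- If the present definition is still wanted, report it as time to progression, with death as a competing risk.

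The cost is wording. Survival is already assessed at the study visits and death dates are needed for OS, so no new data or patients are required. The reported median PFS may be slightly shorter.
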